1.5.2. PROGRESSION-FREE SURVIVAL (Evaluables)

Following the protocol, the population of was used for the efficacy analysis evaluable patients: n = X (see section 1.1)

According to protocol: PFS is defined in each patient as the time between the date of the first dose of ipilimumab and the date on which progression is determined or death occurs, whichever occurs first. If a patient dies without prior notification of progression, progression will be considered to have occurred on the date of death. For a patient who undergoes tumor resection during the study, the PFS will be censored on the date of the last tumor evaluation prior to resection. In the case of patients who remain alive and do not show progression, the PFS will be censored on the date of the last tumor evaluation. For patients in whom PE has been determined before week 12 and a subsequent evaluation of EE, PR, or CR is obtained, the date of PE after response (if available) will be used in the analysis. of the SLP; otherwise, these patients will be censored on the date of their last tumor evaluation.

Table 29. Progression-free survival (evaluable)

Estimated progression-free survival	N events	N at risk	% of patients without progression	95% CI	with progression
at 6 months					
to 12 months					
	N (%)	Median	Min-Max	Standard Error	Confidence interval 95%
Estimated progression-free survival					

Table 30. Progression-free survival and PFS at 6 months (Evaluable)

		N (%; 95% CI)
Progression-free survival	Alive (without PE)	
	PE	
	Exitus (without prior PE)	
	Total	
PFS at 6 months (crude)	No	
	Yes	
	No follow-up at 6 months (or PE before 6m)	
	Total	
PFS at 6 months (crude) (excluding patients with follow-up <6 months and no PE / previous death)	No	
	Yes	
	Total	

Figure 3. Survival free of Estimated progression (Evaluable)

Table 31. Time to PE (only in patients with PE)

	N	Mean (SD)	Median (Min-Max)
Time to PFS (months from 1st cycle of Ipilimumab) (only patients with PE)			

1.5.2.1. PFS RATE A 6 MONTHS vs BASAL CHARACTERISTICS

Next, a univariate and multivariate analysis was proposed. e the possible association between the baseline characteristics and the 6-month progression-free survival rate, using logistic regression models taking PD or death as an event at 6-month follow-up.

A univariate analysis was carried out in which none of the following variables showed a statistically significant association ($p < 0.1$) with PFS at 6 months of follow-up and therefore multivariate analysis was not carried out.

Table 32. Univariate analysis: PFS rate at 6m vs Baseline characteristics

		PFSat 6m		Univariate logistic regression		
		No (without PD or death) N (%)	Yes (living without PD) N (%)	Total N (%)	OR (95% CI)	p-value
Age categorized according to median (66 years)	<66 years					
	≥66 years					
	Total					
Sex	Female					
	Male					
	Total					
KPS	90-100					
	70-80					
	Total					
Barthel Index	15-20					
	<15					
	Total					
Status B-Raf (Current Melanoma)	Native					
	Mutated					
	Total					
No. of lines of previous treatment	0					
	1					
	> 1					
	Total					
Status B-Raf (previous Melanoma)	Native					
	Mutated					
	Total					
Type of locations M1 Current Brain	Single					
	Multiple					
	Total					
Location M1 Current liver	No					
	Yes					
	Total					
Corticosteroids at baseline and / or C1	No					
	Yes					
	Total					

No. of organs with metastatic disease	1	
	2	
	3	
	4	
	Total	
No. of organs with metastatic disease	≤2	
	> 2	
	Total	
Neutrophil / Lymphocyte(quantitative)		
RatioNeutrophil /Ratio Lymphocyte> 3 (high risk)	No	
	Yes	
	Total	
Previous BRAF Inhibitor	No	
	Yes	
	Total	
CRPvalue		
Hemoglobinvalue		
LDH valueLDH value		
> ULN	No	
	Yes	
	Total	
LDH value> 1.5 * ULN	No	
	Yes	
	Total	

-

Table 33 Multivariate analysis: PFS rate at 6m vs Baseline characteristics

		Multivariate logistic regression		
		N ¹	OR (95% CI)	p-value
XXXXXX	No			
	Yes			
XXXXXX	No			
	Yes			
Constant				

1: patients for whom data were not available in all variables included in the multivariate model (n = X).

1.5.3. BEST RESPONSE (Evaluable)

Following the protocol, for the efficacy analysis the population of was used evaluable patients: $n = X$ (see section 1.1)

Table 34. Best response (Evaluable)

		N (%; 95% CI)
Best response (Criteria modified from WHO)	CR	
	PR	
	EE	
	PE	
	NE (Not evaluated)	
	Total	
Best response (Response Criteria related to immunity. CRri)	RCri	
	RPri	
	EEri	
	PEri	
	NEri (Not evaluated)	
	Total	

According to protocol: Overall best response rate (TMRG)

The MRG is defined by a population subgroup as the total number of patients treated in the subgroup whose MRG is CR or PR, divided by the total number of patients treated in the subgroup.

Table 35. TMRG (Evaluables)

		N (%; 95% CI)
TMRG: CR or PR (Modified WHO Criteria)	No	
	Yes	
	Not evaluated	
	Total	
TMRG: CR or PR (Response Criteria related to immunity. CRri)	No	
	Yes	
	Not evaluated	
	Total	

According to protocol: Disease control rate (TBI)

TBI is defined as the total number of patients treated in each subgroup whose GRM is CR, PR or EE, divided by the total number of patients treated in the subgroup.

Table 36. TBI (Evaluable)

		N (%; 95% CI)
TCE: CR or PR or EE (Modified WHO Criteria)	No	
	Yes	
	Not evaluated	
	Total	
TCE: CR or PR or EE (Response Criteria related to immunity. CRri)	No	
	Yes	
	Not evaluated	
	Total	

Table 37. Time to best response (evaluable)

	N ¹	Mean (SD)	Median (Min-Max)
Time to best WHO response (months from 1st cycle of ipilimumab)			
Time to best response CRri (months from 1st cycle of ipilimumab)			

1: Patients with response recorded in CRDe

Table 38. Time to best response (Evaluable) according to MRG

Time to best response	N ¹	Mean (SD)	Median (Min-Max)
Best global response (modified WHO criteria)	CR		
	PR		
	EE		
	PE		
Time to best response	N ¹	Mean (SD)	Median (Min-Max)
Best Overall response (Response Criteria related to immunity. CRri)	RCri		
	RPri		
	EEri		
	PEri		

1: Patients with response recorded in CRDe

According to protocol: Duration of response

The duration of a patient's response is defined as the time elapsed between the date on which the measurement criteria for an overall response of PR or CR are first met (whichever response is recorded first, and if confirmed later) and the date of disease progression or death , whichever comes first. For patients undergoing tumor resection during the study, the duration of response will be censored on the date of the last tumor evaluation prior to resection. In the case of patients who remain alive and do not show progression, the duration of the response will be censored on the date of the last tumor evaluation.

Table 39. Duration of response (Evaluable)

	N ¹	Mean (SD)	Median (Min-Max)
Duration of response (modified WHO criteria), months			
Duration of response (Response Criteria related to immunity. CRri) , months			

1: Patients with response recorded in CRDe

According to protocol: Duration of Stable Disease

The duration of stable disease is defined in patients whose MRG is EE as the time that elapses between the moment when the disease was documented for the first time. EE and date of PE or death (whichever occurs first). In the case of a patient who undergoes tumor resection after week 12 but before disease progression occurs, the duration of stable disease will be censored on the date of the last evaluable tumor evaluation prior to resection. In patients with an EE MRG at week 12, the date of PE after this time (if available) will be used in the analysis of the duration of stable disease. In patients with an EE MRG who have not shown subsequent progression and remain alive, the duration of stable disease will be censored on the date of the last evaluable tumor evaluation.

Table 40. Duration of stable disease (Evaluable)

	N ¹	Mean (SD)	Median
--	----------------	-----------	--------

	(Min-Max)
Duration of stable disease (modified WHO criteria), months	
Duration of stable disease (Response Criteria related to immunity . CRri), months	

1: Patients with response recorded in CRDe

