9.4.2 Efficacy Analyses

9.4.2.1 *Methods for Time to Event Primary Endpoint*

The yearly rate of survivors will be the actual proportion of patients alive after 1 year of the first administration of ipilimumab.

9.4.2.2 *Methods for Time to Event Secondary Endpoints*

The overall survival and event-free survival probabilities will be estimated and plotted using the Kaplan-Meier product-limit method.

Additionally, 1 and 2 year rates will be also based upon Kaplan-Meier estimates along with their corresponding log-log transformed 95% confidence intervals.

The progression-free survival probabilities will also be estimated and plotted using the Kaplan-Meier product-limit method. Duration of response, duration of stable disease, and overall survival in subjects with brain metastasis will also be described using these same Kaplan-Meier methods.

A differential analysis will be done with intracranial and extracranial disease.

9.4.2.3 *Methods for Proportion Based Rates Secondary Endpoints*

For BORR and DCR, descriptive summary statistics (e.g., total number of patients, number and percent responders, 95% confidence interval) will be used. An exact two-sided 95% CI for these rates will be computed. A differential analysis will be done with intracranial and extracranial disease.

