1.5.1. OVERALL SURVIVAL (Evaluable)

Survival Overall (OS) is presented for evaluable patients (n = XX). The estimated overall survival at one year (calculated using Kaplan-Meier) was X% (with a 95% CI: XX%) with a median OS of X months (95% CI XX months).

Table 18. Overall survival (evaluable)

Estimated overall survival	N events	N at risk	% of patients without death	95% CI	% with death
at 6 months					
to 12 months					
	N (%)	Median	Min-Max	Standard Error	95% Confidence interval
Overall survival Estimated					

Table 19. Overall survival: Events and OS at 1 year (Evaluable)

		N (%; 95% CI)
Overall survival	Live	
	Exitus	
	Total	
OS at 1 year (crude)	No	
	Yes	
	No follow-up at 1 year (or death)	
OS at 1 year (gross) (excluding patients with follow-up <1 year and without previous death)	Total	
	No	
	Yes	
	Total	

Figure 1. Estimated overall survival (Evaluable)

Table 20. Time to Exitus (only in patients with death)

	N	Mean (SD)	Median (Min-Max)
Time to Exitus			

Table 21. Reasons for leaving the study (evaluable)

	N (%)
Reason Exitus Progression of the disease	

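### SAP Tables 39 and 40 summarise duration of response and of stable disease by mean and plain median, although the protocol requires Kaplan-Meier and both definitions censor patients

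*SAP*

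**What the plan says.** Protocol section 9.4.2.2 sets the method: "Duration of response, duration of stable disease, and overall survival in subjects with brain metastasis will also be described using these same Kaplan-Meier methods". For fixed time points the same section says: "Additionally, 1 and 2 year rates will be also based upon Kaplan-Meier estimates along with their corresponding log-log transformed 95% confidence intervals".

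SAP section 1.5.3 restates both definitions as being according to protocol, including the censoring. For response it says: "In the case of patients who remain alive and do not show progression, the duration of the response will be censored", at the last tumour evaluation. Resected patients are censored at the last evaluation before surgery. Stable disease has parallel rules.

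The shells beneath those definitions are "Table 39. Duration of response (Evaluable)" and "Table 40. Duration of stable disease (Evaluable)". Each has three columns: N, mean (SD) and median (min-max), with one row for mWHO and one for irRC. The only footnote is "1: Patients with response recorded in CRDe".

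**The concern.** A duration with censored observations cannot be summarised as if every value were complete. The SAP censors patients in the text and then gives tables with nowhere to show a censored value. A programmer working from these shells must either treat censored times as complete or leave those patients out. Neither is the method the protocol chose, and no reason for a departure is given.

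The protocol itself argues that ipilimumab responses are durable (section 1.3.5) and reports that median duration of response was not reached with 3 mg/kg ipilimumab alone in MDX010-20 (section 1.3.5.b). A plain sample median always yields a number, so it could not report that result here. Responders will also be few, so a median without an interval could be read as far more certain than it is.

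**Working it through.** **Shells compared**

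| SAP table | Events | At risk or censored | SE and 95% CI | Who is counted |
|---|---|---|---|---|
| 18 (OS), 29 (PFS) | yes | at risk | yes | evaluable patients |
| 20, 31 | no | no | no | events only, stated in the title |
| 39, 40 | no | no | no | patients with a recorded response |

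Where the SAP intends Kaplan-Meier, the shell shows it. The mean (SD) and median (min-max) layout of Tables 39 and 40 is also that of "Table 20. Time to Exitus (only in patients with death)" and "Table 31. Time to PE (only in patients with PE)", but without the events-only restriction. The text gives the censoring date. What is missing is how a censored time enters the mean and median.

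**Illustration of size.** The plan states no figure to reproduce, so this is a simulation under stated assumptions.

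Inputs:
- Accrual from 03/2014 to 10/2015, 19 months, taken as uniform. Follow-up to 10/2016 gives 12 to 31 months from first dose (synopsis). Closure 18 months after the last first dose gives 18 to 37 months, capped at 36 (Protocol section 3).
- Scans at weeks 12 and 17, then every 9 weeks (Protocol section 6.2.1.e). Response is assumed at week 12, with censoring at the last scan as the definitions require.
- Assumed true medians m: 8.1 and 19.3 months (CA184024, placebo and ipilimumab arms, section 1.3.5.c, taken to be medians) and 11.5 months (MDX010-20, ipilimumab + gp100, section 1.3.5.b).
- Durations assumed exponential, so the true mean is m / ln 2: 8.1 / 0.693 = 11.7; 11.5 / 0.693 = 16.6; 19.3 / 0.693 = 27.8.

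Results in months, shown as follow-up ending 12 / 18 months after the last patient:

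| True median | True mean | Censored | Plain mean | Plain median | Events-only median |
|---|---|---|---|---|---|
| 8.1 | 11.7 | 25% / 15% | 8.8 / 10.0 | 8.0 / 8.1 | 5.5 / 6.5 |
| 11.5 | 16.6 | 36% / 25% | 10.6 / 12.4 | 9.4 / 11.5 | 6.4 / 7.8 |
| 19.3 | 27.8 | 54% / 44% | 12.8 / 15.7 | 12.1 / 15.6 | 7.3 / 9.2 |

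The plain columns treat censored times as complete. The Kaplan-Meier median recovers the assumed true median in every row. Censoring at study closure instead of the last scan changes little: for m = 19.3 the plain median becomes 13.0 / 16.8. The two undeclared readings of the median differ by 1.6 months (8.1 − 6.5) to 6.4 months (15.6 − 9.2) on the same data.

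**Number of responders.** Response rates cited in the protocol include 4.2% (CA184022, 3 mg/kg, Table 10), 5.7% and 10.9% (MDX010-20, ipilimumab + gp100 and ipilimumab alone), and 15.2% (CA184024, 10 mg/kg + dacarbazine). Among 56 patients: 56 × 0.042 = 2.4; 56 × 0.057 = 3.2; 56 × 0.109 = 6.1; 56 × 0.152 = 8.5. With six responders and a true median of 11.5 months, the sample median has a 95% range of about 3.5 to 29 months even without censoring.

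The documents give no duration of stable disease, so no figure is offered for Table 40.

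**The case against.** The events-only reading is the less likely one. The footnote counts patients with a recorded response, the text gives ongoing patients a duration, and the SAP labels a table when it wants events only. On the likelier reading the plain median is barely biased at 8.1 months and at most about 2 months low at 11.5. The large gap needs 19.3 months, which comes from a different dose and population. This stands, and the events-only column should be read with it in mind. It does not rescue the mean, which is low in every row.

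The median cell might be meant for a Kaplan-Meier median, since Tables 18 and 29 also have median and min-max cells, and SAP text before section 1.2 was not available for this check. But nothing in section 1.5.3 says so, and a mean (SD) column is not Kaplan-Meier output.

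Kaplan-Meier would add little precision for so few responders. In a simulation of the same set-up, the upper log-log limit for the median was never estimable with 3 or 6 responders, and was missing in 37% to 96% of runs with 9. That is true, but an open upper limit tells the reader how little is known, which a bare median hides. Table 40 may have more patients.

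Finally, both endpoints are descriptive and absent from the objectives in Protocol section 2.2, and the swimmer plot (SAP Figure 13) would show each patient's status at the end of follow-up. This limits the weight of the point. The plot gives no estimate or interval, and its section covers WHO response only.

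**Conclusion.** The concern holds. Tables 39 and 40 depart from Protocol section 9.4.2.2 without explanation and do not fit the censoring rules printed above them. If any response or stable disease is ongoing or resected, the mean will be too low under either reading. The plain median is too low only when substantial censoring falls before it. In the illustration the plain mean is about 15% to 54% below the true mean (10.0 against 11.7; 12.8 against 27.8), and the plain median ranges from unbiased to about 7 months low (12.1 against 19.3). These sizes rest on exponential durations, response at week 12, uniform accrual and durations borrowed from other trials. The direction for the mean does not depend on them. The primary 1-year survival analysis is unaffected. This should be corrected before the tables are produced, but it does not threaten the trial's main conclusion.

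**What to change.** Replace the shells of Tables 39 and 40, for both mWHO and irRC, with N, number of events, number censored, Kaplan-Meier median with 95% CI (allowing an entry of not reached), and 1- and 2-year rates with log-log 95% CI. Show the number at risk beside the rates, because the 2-year figures may rest on very few patients. Mark censored values in the range and drop the mean (SD). Add a sentence stating that ongoing and resected patients enter as censored at the date given in each definition. If the sponsor prefers another summary, the SAP should record and justify the departure from the protocol. The cost is two table shells and one sentence; the same data are used.

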1.5.4. GRAPHIC REPRESENTATIONS RESPONSE (Evaluable)

Following the researcher's instructions, different graphic representations have been elaborated to evaluate the results of the response (WHO).

Figure 4. Spider plot: Absolute change in the measurements of the lesions with respect to baseline

Figure 6. Waterflow plot: Absolute change in the measurements of the lesions with respect to baseline (according to the use of corticosteroids)

Figure 7. Waterflow plot: Absolute change in the measurements of the lesions with respect to baseline (excluding extreme value) (according to the use of corticosteroids)

Figure 8. Waterflow plot:% change in the measurements of the lesions with respect to baseline (according to the use of corticosteroids)

Figure 9. Waterflow plot:% change in the measurements of lesions with respect to baseline (according to use of corticosteroids) cut by 200%

Figure 10. Waterflow plot:% change in the measurements of lesions with respect to baseline (excluding extreme value) (according to use of corticosteroids)

Figure 11. Waterflow plot:% change in lesion measurements with respect to baseline (according to response)

Figure 12. Waterflow plot:% change in lesion measurements with respect to baseline (excluding extreme value) (according to answer)

Figure 13. Swimmerplot: follow-up Entity of each patient with corticosteroids, response and status at the end of follow-up

1.6. TOXICITIES (Treatment-related AEs)

As specified in the protocol for this analysis, was used the population of treated patients, n = XX.

Table 41. Toxicities

		N (% ¹ ; 95% CI)
Patients with at least one toxicity, any grade	No	
	Yes	
	Total	
Patients with at least one gradetoxicity≥3	No	
	Yes	
	Total	
Patients with grade 3 toxicities	No	
	Yes	
	Total	
Patients with grade toxicities 4	No	
	Yes	
	Total	
Patients with grade 5 toxicities	No	
	Total	
No. of gradetoxicities≥3per patient ¹	None	
	1 toxicity	
	2 toxicities	
	3 toxicities	
	4 toxicities	
	Total	

1: Patients could present more than one toxicity of the same grade

Table 42. Time between initiation of treatment and toxicity (days)

	Mean (SD)	Median (Min-Max)
Time between initiation of treatment and toxicity (days)		

The frequencies of toxicities with grade ≥3 are shown below.

Table 43. Toxicities with grade ≥3

Type of Toxicity	Grade 3 N (% ¹)	Grade 4 N (% ¹)

1:% calculated with respect to the total number of patients evaluable for safety (n = XX)

Below is a list of the toxicities with grade \geq 3 per patient with their characteristics.

Table 44. List of grade \geq 3 toxicities (patients may present more than one toxicity)

Patient code	Toxicity and Grade	SAE	Relationship with treatment	Start	date AE End date AE

The most frequent toxicities with their degrees and in ANNEX I : LIST OF TOXICITIES A list of all toxicities is presented.

Table 45. Most frequent toxicities (> 10% on = 5) and their grade

		N (%)
XXXX	Absence	
	Presence	
XXXX	Absence	
	Presence	

Table 46. Median time between initiation of treatment and toxicity in the most frequent toxicities (days)

Time between initiation of treatment and toxicity	
Type of toxicity (most frequent)	Median (days)

Table 47. Median time between the start of treatment and toxicity in the most frequent toxicities (days) as a function of the MRG rate

Type of Toxicity		Rate of best global response TMRG (PR or CR) (modified WHO criteria)	Median (days)
Adverse Event	XXXX	No	
		Yes	
		Total	
	XXXX	No	
		Yes	
		Not evaluated	
		Total	

